6.3.1.1 Change in patient's weight

The dose of study drug will only be recalculated using Dosing [Table 6-2](#) and [Table 6-3](#) (DFX DT), and [Table 6-4](#) and [Table 6-5](#) (DFX FCT) during the study if the change (increase or decrease) in body weight exceeds 10% of the weight compared to the Randomization Visit or the last dose adjustment due to change in patient's body weight.

6.3.1.2 Elevations in serum creatinine

Serum creatinine should be monitored during the study as stated in the visit evaluation schedule [Table 7-1](#).

During the treatment period, patients who develop an increase in serum creatinine $\geq 33\%$ above their baseline value (average of visit 1 and 2) resulting in a serum creatinine above the upper limit of normal (ULN), on two consecutive occasions, the dose of the study drug will be reduced to 5 mg/kg/day for DFX DT and 3.5 mg/kg/day for DFX FCT until serum creatinine returns to below the age adjusted ULN.

It is recommended to check fluid balance and ensure adequate hydration of the patient.

In case of a single increase in serum creatinine, the assessment will be repeated in 2 weeks.

If after a dose reduction, a progressive increase in serum creatinine beyond the age adjusted ULN is observed, a treatment interruption is recommended.

After an interruption, if serum creatinine falls below the age appropriate ULN range on two consecutive visits, it is recommended to resume DFX DT therapy at 5 mg/kg/day or DFX FCT therapy at 3.5 mg/kg/day, and after 1 month, if the serum creatinine increase does not recur, study medication can be re-escalated to the standard dose of DFX DT at 10 mg/kg/day or DFX FCT at 7 mg/kg/day.

Caution should especially be used in patients with CrCl between 40 and less than 60 mL/min, particularly in cases where there are additional risk factors that may impair renal function such as concomitant medications, dehydration, or severe infections.

DFX therapy must be discontinued in case serum creatinine >2 times the age-appropriate upper limit or if CrCl <40 mL/min.

[figure not shown]
If after dose reduction, a progressive increase in serum creatinine is observed, Novartis must be contacted.

6.3.1.3 Skin disorders

6.3.1.3.1 Stevens-Johnson syndrome (SJS)

Severe skin reactions, including Stevens-Johnson syndrome (SJS), have been reported during DFX therapy.

If Stevens Johnson syndrome is suspected, study treatment must be immediately discontinued and not be reintroduced.

6.3.1.3.2 Skin Rash other than SJS

For skin rash of mild/moderate severity (defined as those causing minimal symptoms which require no or minimal supportive treatment), study drug should be continued without dose adjustment. The skin rash may resolve spontaneously without further intervention.

If the rash persists for >1 week or becomes more severe, hold study drug. After the rash resolves, resume study drug at 50% of patient's dose. If the rash does not recur, increase dose back to 10 mg/kg/day for DFX DT or 7 mg/kg/day for DXF FCT after 2 weeks.

For a severe rash (distressing symptoms requiring discontinuation and/or systemic steroids), discontinue treatment until resolution of rash. Once the rash has resolved, resume at 50% of patient's dose. If necessary, a brief course of oral steroids may be given concurrently with resumption of study drug. If the rash does not recur, increase to initial dose of 10 mg/kg/day for DFX DT or 7 mg/kg/day for DFX FCT.

If the rash recurs, study drug may be discontinued if the investigator believes that it is in the best interest of the patient.

Novartis may be contacted by the investigator to discuss dosing options if the investigator desires.

6.3.1.4 Increased liver enzyme levels

If there is a persistent and progressive increase in serum transaminase levels that cannot be attributed to other causes, DFX should be interrupted. Once the cause of the liver function test abnormalities has been identified or after a return to normal levels, cautious re-initiation of DFX DT treatment at 5 mg/kg/day dose followed by dose escalation up to 10 mg/kg/day or re-initiation of DFX FCT treatment at 3.5 mg/kg/day dose followed by dose escalation up to 7 mg/kg/day may be considered. In cases of a second rise in serum transaminase levels, the investigator should contact Novartis.

[figure not shown]
6.3.1.5 Hepatic Impairment

Patients with hepatic impairment fulfilling criteria of Child-Pugh Class B or C are not allowed to enter the study.

In patients developing moderate hepatic impairment (Child-Pugh Class B) during study, study treatment will be interrupted and the patient will be discontinued from study.

6.3.1.6 Dose modification criteria for auditory (decreased hearing) and ocular (lens opacities) disturbances

Auditory (decreased hearing) and ocular (lens opacities) disturbances have been reported with DFX treatment. Auditory and ophthalmic testing (including fundoscopy) is recommended before the start of DFX treatment. If disturbances occur during study, dose reduction of DFX DT to 5 mg/kg/day or DFX FCT to 3.5 mg/kg/day or interruption may be considered.

6.3.1.7 Dose modification criteria for hypersensitivity reactions

Cases of serious hypersensitivity reactions (such as anaphylaxis and angioedema) have been reported in patients receiving DFX, with the onset of the reaction occurring in the majority of cases within the first month of treatment. If reactions are severe, DFX should be discontinued and appropriate medical intervention instituted.

6.3.1.8 Dose modification criteria for cytopenias

There have been post-marketing reports (both spontaneous and from clinical trials) of cytopenias in patients treated with DFX. Most of these patients had pre-existing hematological disorders that are frequently associated with bone marrow failure. The relationship of these episodes to treatment with DFX is uncertain. In line with the standard clinical management of such hematological disorders, blood counts should be monitored regularly. Dose interruption of treatment with DFX should be considered in patients who develop unexplained cytopenia. Reintroduction of therapy with DFX may be considered, once the cause of the cytopenia has been identified.

6.3.2 Treatment interruption and treatment discontinuation

Patients who permanently discontinue study drug before completing the study should be scheduled for a visit as soon as possible, at which time all of the assessments listed for the final visit will be performed. The Study Treatment Completion eCRF should be completed, documenting the date and reason for stopping randomized study treatment. Any safety finding that leads to discontinuation of study drug should be captured on the AE eCRF.

[figure not shown]
All patients who discontinue study drug, including those who refuse to return for a final visit, will be contacted by the investigational site for safety evaluations during the 30 days following the last dose of study drug.

Patients who discontinue study drug should be considered withdrawn from the study after the final visit assessments are performed or when it is clear that the patient will not return for these assessments.

All patients must be followed for AEs and SAEs for 30 days after the last dose of study treatment. Patients lost to follow up should be recorded as such on the eCRF. For patients who are lost to follow-up, the investigator should show “due diligence” by documenting in the source documents steps taken to contact the patient, e.g., dates of telephone calls, registered letters, etc.

6.3.3 Follow-up for toxicities

Patients whose treatment is interrupted or permanently discontinued due to an AE or abnormal laboratory value must be followed at least once a week for 4 weeks, and subsequently at 4-week intervals, until resolution or stabilization of the event, whichever comes first.

6.3.4 Anticipated risks and safety concerns of the study drug

Appropriate eligibility criteria and specific DLT definitions, as well as specific dose modification and stopping rules are included in this protocol. Preclinical toxicity and/or clinical data can be found in the DFX Investigator's Brochure and Summary of Product Characteristics of EPO.

6.4 Concomitant medications

6.4.1 Permitted concomitant therapy

The concomitant administration of DFX and vitamin C has not been formally studied. Doses of vitamin C up to 200 mg/d have not been associated with adverse consequences.

Any investigational drug other than study medication is NOT permitted during the study.

The investigator must instruct the patient to notify the study site about any new medications (including over-the-counter products) he/she takes after the start of the study drug. All medications (other than study drug) and significant non-drug therapies (including physical therapy and herbal / natural) administered after the patient starts treatment with study drug must be listed on the Concomitant medications/Significant non-drug therapies after start of study drug eCRF.

6.4.2 Permitted concomitant therapy requiring caution and/or action

- Aluminium containing antacid therapies should be avoided because they may bind to DFX.
- The concomitant use of DFX with potent UGT inducers (e.g. rifampicin, phenytoin, phenobarbital, ritonavir) may result in a decrease in DFX efficacy.

Caution must be exercised in patients who are taking study drug in combination with the following drugs:

- Concomitant administration of DFX with drugs that have known ulcerogenic potential, such as NSAIDs, corticosteroids, or oral bisphosphonates, and use of DFX in patients receiving anticoagulants may increase the risk of gastrointestinal irritation
- DFX, as a weak CYP3A4 inducer, may potentially decrease serum levels of substances metabolised through CYP3A4 (e.g. cyclosporin, simvastatin, hormonal contraceptive agents)
- DFX is a moderate inhibitor of CYP2C8 and therefore it may increase serum concentrations of substances metabolised through CYP2C8 (e.g. repaglinide, paclitaxel)
- DFX can potentially increase the exposure of the concomitantly administered CYP1A2 substrates that have a narrow therapeutic index (e.g. theophylline, clozapine, tizanidine). Therefore the concomitant administration is not recommended. When deferiasirox and theophylline are used concomitantly, monitoring of theophylline concentration and theophylline dose reduction should be considered.
- The concomitant use of bile acid sequestrants (e.g. cholestyramine, colestevan, colestipol) decreases deferiasirox systemic exposure.

6.4.3 Prohibited concomitant therapy

Concomitant iron therapy is not allowed during the study.

Any investigational drug other than study medication is NOT permitted during the study.

6.5 Patient numbering, treatment assignment or randomization

6.5.1 Patient numbering

Each patient is identified in the study by a Patient Number, that is assigned when the patient is first enrolled for screening and is retained as the primary identifier for the patient throughout his/her entire participation in the trial. The Patient Number consists of [REDACTED]

[REDACTED] so that each patient is numbered uniquely across the entire database. Upon signing the informed consent form, the patient is assigned to the next sequential Patient Number.

The investigator or designated staff will contact the IWR and provide the requested identifying information for the patient to register them into the IWR. Once assigned, the Patient Number must not be reused for any other patient and the Patient Number for that individual must not be changed, even if the patient is re-screened. If the patient fails to be randomized or start treatment for any reason, the reason will be entered into the Screening Log.

IWR must be notified within 2 days that the patient was not randomized.

6.5.2 Treatment assignment or randomization

[figure not shown]
Patients will be assigned to one of the 2 treatment arms ([Section 4.1](#) and [Section 6.1](#)) in a ratio of 1:1.

The randomization numbers will be generated using the following procedure to ensure that treatment assignment is unbiased and concealed from patients and investigator staff. A patient randomization list will be produced by the Interactive Web Response Technology (IWR) provider using a validated system that automates the random assignment of patient numbers to randomization numbers. These randomization numbers are linked to the different treatment arms.

Prior to dosing, all patients who fulfill all inclusion/exclusion criteria will be randomized via IWR to one of the treatment arms. The investigator or his/her delegate will log on to the IWR and confirm that the patient fulfills all the inclusion/exclusion criteria.

6.5.3 Treatment blinding

This is an open-label study and therefore patients, investigators, study site staff and study field monitors are not blinded to the study treatment.

6.6 Study drug preparation and dispensation

The investigator or responsible site personnel must instruct the patient or caregiver to take the study drugs as per protocol. Study drug(s) will be dispensed to the patient by authorized site personnel only. All dosages prescribed to the patient and all dose changes during the study must be recorded on the Dosage Administration Record CRF.

6.6.1 Study drug packaging and labeling

DFX and EPO can be provided as local commercial material or global clinical supply where appropriate and as per local regulations. Global clinical supply will be provided as open supply, and will be packed and labeled under the responsibility of [REDACTED]. Study treatment labels will be available in the local language and comply with the legal requirements of each country. They will include storage conditions for the medication but no information about the patient.

If DFX and/or EPO are sourced and labeled in-country, the locally approved form and packaging of DFX and/or EPO will be used.

As per Novartis procedures, investigational treatment will only be shipped directly to the investigational sites.

DFX and/or EPO in different formulations and strengths can be used once they are approved.

Refer to the latest [Investigator Brochure for DFX] or local product information for dosing instructions and storage conditions.

6.6.2 Drug supply and storage

Study treatments must be received by designated personnel at the study site, handled and stored safely and properly, and kept in a secured location to which only the investigator and designated site personnel have access. Upon receipt, the study treatment should be stored according to the instructions specified on the drug labels.

[figure not shown]
6.6.3 Study drug compliance and accountability

6.6.3.1 Study drug compliance

Compliance will be assessed by the investigator and/or study personnel at each patient visit and information provided by the patient and/or caregiver will be captured in the Drug Accountability Form. This information must be captured in the source document at each patient visit.

6.6.3.2 Study drug accountability

The investigator or designee must maintain an accurate record of the shipment and dispensing of study treatment in a drug accountability log. Drug accountability will be noted by the field monitor during site visits and at the completion of the study. Patients will be asked to return all unused study treatment and packaging on a regular basis, at the end of the study or at the time of study treatment discontinuation.

At study close-out, and, as appropriate during the course of the study, the investigator will return all used and unused study treatment, packaging, drug labels, and a copy of the completed drug accountability log to the Novartis monitor or to the Novartis address provided in the investigator folder at each site.

6.6.3.3 Handling of other study treatment

Not applicable.

6.6.4 Disposal and destruction

All unused study drug supply must be destroyed. The study drug supply can be destroyed at the local Novartis facility, Drug Supply group or third party, as appropriate. Study drug supply may only be destroyed at the site if permitted by local regulations and authorized by Novartis in a prior agreement.

7 Visit schedule and assessments

7.1 Study flow and visit schedule

Following registering in IWR for screening, patient eligibility will be checked once all screening procedures are completed. The eligibility check will be embedded in the IWR system. Details guidelines to be followed can be found in the IWR manual.

Table 7-1 lists all of the assessments and indicates with an “X”, the visits when they are performed. All data obtained from these assessments must be supported in the patient’s source documentation. Assessments such as laboratory data will be transferred to the database electronically. The table indicates which data are entered into the database (D) or remain in source documents only (S) (column category).

[figure not shown]
[figure not shown]
[figure not shown]

Table 7-1 Visit evaluation schedule

Visit	Category	Protocol Section	Screening 1	Screening 2	Treatment Period											Follow-up period	
					Randomization		Cycle 1		Cycle 2		Cycle 3	Cycle 4	Cycle 5	Cycle 6	End of study treatment (EOT)	30-day Safety Follow-up	Study evaluation completion
Week			1	2	3	4	5	6	7	8 ³	9	10	11	12	777	501	778
Obtain Informed Consent	D	7.1.1.3	X														
Inclusion/exclusion criteria	D	7.1.1.3	X	X													
Demography	D	7.1.1.3	X														
IWR	D	6.5.2	X		X										X		
Medical history	D	7.1.1.3	X														
Physical examination	S	7.2.2.1	X		X	X	X	X	X		X	X	X	X	X		
Height (cm)	D	7.2.2.3	X														
Weight (kg)	D	7.2.2.3	X		X				X		X	X	X	X	X		
Vital signs ¹	D	7.2.2.2	X	X	X	X	X	X	X		X	X	X	X	X		
Transfusion/RBC History	D	7.1.1	X														
FAB classification	D	7.1.1.3	X														
ECG	D	7.2.2.5.1	X														
Ocular Exam ²	D	7.1.1.3	X														
Audiometry ²	D	7.1.1.3	X														
Laboratory Assessments		7.2.2.4															
Hematology	D	7.2.2.4.1	X	X	X		X		X	X ³	X	X	X	X	X		
Biochemistry	D	7.2.2.4.2	X	X	X	X	X	X	X		X	X	X	X	X		

[figure not shown]

	Category	Protocol Section	Screening 1	Screening 2	Treatment Period											Follow-up period	
					Randomization	Cycle 1		Cycle 2		Cycle 3	Cycle 4	Cycle 5	Cycle 6	End of study treatment (EOT)	30-day Safety Follow-up	Study evaluation completion	
Visit			1	2	3	4	5	6	7	8 ³	9	10	11	12	777	501	778
Week			-4 to -1	1	2	3	4	5	7	9	13	17	21	25			
Hepatitis Viral	D	7.2.2.4.5	X														
Serum Ferritin ⁴	D	7.2.2.4.2	X	X	X				X		X	X	X	X	X		
FE/TIBC (TSAT)	D	7.2.2.4.2	X		X	X	X	X	X		X	X	X	X	X		
Endogenous EPO	D	7.2.2.4.2	X														
B12	D	7.2.2.4.2	X														
Folate	D	7.2.2.4.2	X														
Serum Creatinine ⁵	D	7.2.2.4.2	X	X	X	X	X	X	X		X	X	X	X	X		
ALT/AST	D	7.2.2.4.2	X	X	X	X	X	X	X		X	X	X	X	X		
Direct/Indirect/Total bilirubin	D	7.2.2.4.2	X	X	X	X	X	X	X		X	X	X	X	X		
Alkaline phosphatase	D	7.2.2.4.2	X	X	X	X	X	X	X		X	X	X	X	X		
Creatinine Clearance ⁶	D	7.2.2.4.2	X	X	X	X	X	X	X		X	X	X	X	X		
Urine dipstick ⁷	D	7.2.2.4.3	X		X	X	X	X	X		X	X	X	X	X		
Microscopic urine ⁷	D	7.2.2.4.3	Only if medically indicated in case of positive dipstick														
Urinary protein/creatinine ratio	D	7.2.2.4.3	X	X	X	X	X	X	X		X	X	X	X	X		
Serum pregnancy test ⁸	D	7.2.2.4.4		X											X		
Urinary pregnancy test ⁸	D	7.2.2.4.4			X				X		X	X	X	X			
Blood pressure self-monitoring ¹	S		-----continuous-----														

Visit	Category	Protocol Section	Screening 1	Screening 2	Treatment Period											Follow-up period	
					Randomization	Cycle 1		Cycle 2		Cycle 3	Cycle 4	Cycle 5	Cycle 6	End of study treatment (EOT)	30-day Safety Follow-up	Study evaluation completion	
Week			1	2	3	4	5	6	7	8 ³	9	10	11	12	777	501	778
Concomitant medication	D	6.4	X	X	X	X	X	X	X		X	X	X	X	X		
Adverse events ¹⁰	D	8.1	X	X	X	X	X	X	X	X	X	X	X	X	X	X	
Drug Dispensing	D	6.6.3			X				X		X	X	X	X			
Drug Accountability DFX	D	6.6.3							X		X	X	X	X	X		
Drug Accountability EPO	S	6.6.3							X		X	X	X	X	X		
Study Evaluation completion (SEC)	D																X

¹ Blood pressure has to be measured before each dose of EPO. EPO needs to be hold if BP >160/80.
² Ocular and Audiometry examinations must be performed at screening, should a patient have evidence at the Screening Visit that the examination(s) were performed 6 months prior to screening then the examination(s) do not need to be repeated. The examination(s) can be performed at any time at the investigators discretion if symptomatically/clinically indicated.
³ Visit 8 has to be performed only if EPO dose was increased at Visit 7. Then hematology parameters have to be assessed at Visit 8.
⁴ Serum ferritin: Two samples at screening done at least 14 days apart. The serum ferritin samples should be obtained in the absence of known infection.
⁵ Serum creatinine will be measured at Screening Visit 1 and Screening Visit 2 and the mean value will be used for eligibility criteria. Serum creatinine will also be measured weekly between the Randomization Visit and Week 4 visit.
⁶ Creatinine clearances will be calculated by the central laboratory at every visit.
⁷ Microscopic analysis will be performed only in case of positive dipstick. Dipsticks will be supplied by the central lab.
⁸ Required for Females only.
¹⁰ Adverse events must be followed up for 30 days after the last dose of study treatment.

7.1.1 Screening

Prior to commencement of the screening examination, the patient must have given full informed consent and have completed the study Informed Consent form. Once this has been signed and dated by the patient then the investigator can take the patient through the study inclusion and exclusion criteria to make sure that the patient is fully eligible to participate.

The full list of assessments to be performed during the screening period (week -4 to week -1) is detailed in [Table 7-1](#) and [Table 7-2](#). Two Screening Visits that are at least 14 days apart are needed to perform key safety parameters prior to first dose administration as specified in the label.

Re-screening is permissible on a case by case basis. Please contact Novartis for guidance and see [Section 7.1.1.2](#) to get information on how to process screen failures.

7.1.1.1 Eligibility screening

Patient eligibility will be confirmed by the site monitor during the second monitoring visit.

7.1.1.2 Information to be collected on screening failures

Patients who sign an informed consent but fail to be started on treatment for any reason will be considered a screen failure. The reason for not being started on treatment will be entered on the Screening Log and each patient's demographic information will be on the Demography CRF.

[figure not shown]
If the patient fails to be randomized, the IWR must be notified within 2 days of the screen fail that the patient was not randomized.

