8.1 Adverse events

8.1.1 Definitions and reporting

An adverse event is defined as the appearance of (or worsening of any pre-existing) undesirable sign(s), symptom(s), or medical condition(s) that occur after patient's signed informed consent has been obtained.

Abnormal laboratory values or test results occurring after informed consent constitute adverse events only if they induce clinical signs or symptoms, are considered clinically significant, require therapy (e.g., hematological abnormality that requires transfusion or hematological stem cell support), or require changes in study medication(s).

Except for screening failures, adverse events that begin or worsen after informed consent should be recorded in the Adverse Events CRF. Conditions that were already present at the time of informed consent should be recorded in the Relevant Medical History/Current Medical Conditions CRF of the patient's CRF. Adverse event monitoring should be continued for at least 30 days (or 5 half-lives, whichever is longer) following the last dose of study treatment. Adverse events (including lab abnormalities that constitute AEs) should be described using a diagnosis whenever possible, rather than individual underlying signs and symptoms. When a clear diagnosis cannot be identified, each sign or symptom should be reported as a separate Adverse Event.

Severity of adverse events will be assessed as mild, moderate, or severe. Information about deaths will be collected through an EOT form.

The occurrence of adverse events should be sought by non-directive questioning of the patient (subject) during the screening process after signing informed consent and at each visit during the study. Adverse events also may be detected when they are volunteered by the patient (subject) during the screening process or between visits, or through physical examination, laboratory test, or other assessments. As far as possible, each adverse event should be evaluated to determine:

1. The severity grade (mild moderate, or severe)
2. Its duration (Start and end dates or Ongoing at End of Study)
3. Its relationship to the study treatment (Reasonable possibility that AE is related: No, Yes)
4. Action taken with respect to study or investigational treatment (none, dose adjusted, temporarily interrupted, permanently discontinued, unknown, not applicable)
5. Whether medication or therapy was given (no concomitant medication/non-drug therapy, concomitant medication/non-drug therapy)

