10.1 Analysis sets

10.1.1 Full Analysis Set

The Full Analysis Set (FAS) comprises all patients to whom study treatment has been assigned by randomization (EPO or EPO+DFX). According to the intent to treat principle, patients will be analyzed according to the treatment they have been assigned to during the randomization procedure.

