2.3 Analysis sets

The analysis will consider the following populations:

Full Analysis Set: The Full Analysis Set (FAS) comprises all patients to whom study treatment has been assigned by randomization (EPO or EPO+DFX). According to the intent to treat principle, patients will be analyzed according to the treatment they have been assigned to during the randomization procedure.

Safety Set: The Safety Set includes all randomized patients who received at least one dose of study medication, i.e. either EPO or EPO+DFX, and with at least one post-baseline safety assessment (e.g. lab, vital signs, AEs) and the statement that a subject did not experience an AE can currently be regarded as a valid safety assessment.

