2.6.1 Patient disposition

This analysis will provide the number and percentage of patients who:

1. Have been randomized (Treated/ Untreated),
2. Have completed the study (patient who completes treatment duration as per protocol as per the EOT [777] page of CRF and also completes the follow up phase as per protocol in the EOS [778] page of CRF),

The number (%) of patient by reason of study treatment discontinuation will be provided for those patients who have discontinued the study treatment. Similarly, this will be performed for study discontinuation. Protocol deviations will be summarized and listed.

The study will end when the last patient will have either withdrawn (including follow-up of 30 days) from the study or completed the study (24 weeks + follow up period of 30 days) from the start of treatment (EPO or EPO+DFX), whichever occurs earlier.

Listings will be provided for screen failure patients (with reasons for screen failure). Screen failures are patients who have been screened (patients who have signed ICF) and who failed to be randomized and treated for any reason (i.e. failing to meet inclusion or exclusion criteria or any other screening procedure).

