E04	B12 or folate deficiency with or without clinical symptoms	Report as PD, include in FAS and Safety Set.

E05	Uncontrolled seizures	Report as PD, include in FAS and Safety Set.
E06	Uncontrolled hypertension	Report as PD, include in FAS and Safety Set.
E07	History of other malignancies and has not been confirmed disease free for ≥ 3 years	Report as PD, include in FAS and Safety Set.
E08	Significant medical condition interfering with the ability to partake in this study	Report as PD, include in FAS and Safety Set.
E09	Thromboembolic event within the past 3 years	Report as a PD, include in FAS and Safety Set.
E10	Known allergic reaction to EPO or human serum albumin	Report as PD, include in FAS and Safety Set.
E11	Clinical or laboratory evidence of active Hepatitis B or Hepatitis C (HBsAg in the absence of HBsAb OR HCV Ab positive with HCV RNA positive)	Report as PD, include in FAS and Safety Set.
E12	Patient has known HIV-1 seropositivity	Report as PD, include in FAS and Safety Set.
E13	Clinically significant anemia resulting from iron deficiencies, autoimmune or hereditary hemolysis, or gastrointestinal bleeding	Report as PD, include in FAS and Safety Set.
E14	Active bleeding	Report as PD, include in FAS and Safety Set.
E15	Patient is pregnant or nursing	Report as PD, include in FAS and Safety Set.
E16	Female of childbearing potential with missing serum HCG test	Report as PD, include in FAS and Safety Set.
E17	Patient with child-bearing potential without adequate birth control	Report as PD, include in FAS and Safety Set.
E19	Hepatic impairment fulfilling criteria of Child-Pugh Class B or C	Report as PD, include in FAS and Safety Set.
G04	Blood Sample for Hematology not collected for analysis at the required visit	Report as PD, include in FAS and Safety Set.
S01	Patient not exposed to study medication	Report as PD, include in FAS and Safety Set.
S02	Epo dose is not stopped as per protocol for more than 1 week but Hb increase is ≥ 1 g/dL and total Hb ≥ 12 g/dL in period week 1-24	Report as PD, include in FAS and Safety set.

S19	Epo dose is stopped for more than 1 week but Hb increase is not ≥ 1 g/dL and total Hb not ≥ 12 g/dL in period week 1-12	Report as PD, include in FAS and Safety Set.
S20	Epo dose is stopped for more than 1 week but Hb increase is not ≥ 1 g/dL and total Hb not ≥ 12 g/dL in period week 13-24	Reported as PD, include in FAS and Safety Set.

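### SAP deviation code S01 places never-dosed patients in the Safety Set against that set's own definition, and the protocol's screen-failure label adds a smaller conflict

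*Protocol*

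**What the plan says.** **Safety Set.** SAP 2.3 reads "The Safety Set includes all randomized patients who received at least one dose of study medication" and adds the need for a post-baseline safety assessment. Protocol 10.1.2 has the same definition.

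**Code S01.** In SAP 4.4, Table 4-7, this code is described as "Patient not exposed to study medication". The action column says to report the deviation and keep the patient in the FAS and the Safety Set.

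**FAS.** Under Protocol 10.1.1 the FAS "comprises all patients to whom study treatment has been assigned by randomization (EPO or EPO+DFX"). SAP 2.3 repeats this. Neither document attaches a dosing condition.

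**Screen failure.** Protocol 7.1.1.2 states: "Patients who sign an informed consent but fail to be started on treatment for any reason will be considered a screen failure". Protocol 6.5.1 points the same way: "If the patient fails to be randomized or start treatment for any reason, the reason will be entered into the Screening Log". SAP 2.6.1 describes screen failures as consented patients "who failed to be randomized and treated for any reason", followed by a parenthesis that refers to screening reasons. The same SAP section has a disposition row for patients who "Have been randomized (Treated/ Untreated").

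**Adverse event recording.** Protocol 8.1.1 states: "Except for screening failures, adverse events that begin or worsen after informed consent should be recorded in the Adverse Events CRF".

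**The concern.** A patient who is randomised and then never takes a dose receives two incompatible instructions for the Safety Set: the definition excludes the patient and S01 includes the patient. SAP 2.10 runs all safety analyses on that set, and SAP 2.5 takes the number in the relevant population as the default denominator. Whichever instruction the programmer follows therefore fixes the denominator of every adverse event percentage.

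The error has a known direction. An undosed patient cannot have a treatment-emergent event, so following S01 can only lower the rates. It does so more in the arm with more undosed patients. In an open-label trial the two arms may differ in this respect.

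Separately, the protocol's screen-failure wording applies to the same patient. A site that follows it would enter the patient on the Screening Log, collect demography and record no adverse events on the CRF. The SAP, meanwhile, counts the patient among those randomised.

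**Working it through.** **1. Planned figures.** The plan gives no figure for undosed patients. Its only planning figures are the confidence intervals in Protocol 10.8 and SAP 2.11. The first is matched by 0.20 ± 1.96 × √(0.6 × 0.4/32 + 0.4 × 0.6/32) = 0.20 ± 0.24 = (−0.04, 0.44). The inputs are the assumed response rates and 30 + 2 per arm. No Safety Set quantity enters, so S01 cannot alter any planned figure.

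**2. Where each rule puts a randomised, never-dosed patient.**

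| Rule | FAS | Safety Set |
|---|---|---|
| Protocol 10.1.1 and 10.1.2 | in | out |
| SAP 2.3 | in | out |
| SAP Table 4-7, S01 | in | **in** |

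The FAS column agrees throughout. The Safety Set column does not.

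**3. Direction.** The on-treatment period starts on the day of first dose (Protocol 10.5.11.1, SAP 2.10.1). Adverse event summaries count only events that start or worsen in that period (Protocol 10.5.11.2, SAP 2.10.2). An undosed patient therefore adds 0 to the numerator and, under S01, 1 to the denominator.

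**4. Size for adverse events.** Inputs: about 60 patients at 1:1, so 30 per arm (Protocol 10.8, SAP 3.2). The number undosed, k, is not given; I assume 1 to 3 in one arm. For x patients with an event, the rate is x/30 under S01 and x/(30 − k) under the definition. The gap is xk/[30(30 − k)].

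| Patients with event | S01: x/30 | k = 1: x/29 | k = 2: x/28 | k = 3: x/27 |
|---|---|---|---|---|
| 3 | 10.0% | 10.3% | 10.7% | 11.1% |
| 12 | 40.0% | 41.4% | 42.9% | 44.4% |
| 15 | 50.0% | 51.7% | 53.6% | 55.6% |
| 24 | 80.0% | 82.8% | 85.7% | 88.9% |

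For 15 patients the gap is 15/870 = 1.7 points at k = 1 and 45/810 = 5.6 points at k = 3.

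**5. Exposure.** SAP 2.7.1 also uses the Safety Set and sets exposure to zero for patients who took no study drug. Adding k zeros multiplies the arm mean by (30 − k)/30, which is 0.967 at k = 1 and 0.900 at k = 3. The percentage of exposure in the same section divides by the duration of exposure, so for an undosed patient it becomes 0/0.

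**6. Response.** The primary analysis is on the FAS (SAP 2.9.1.2). By step 2 the arm has 30 patients under every rule, so 12 responders are 12/30 = 40.0% whichever instruction is followed.

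**The case against.** The best defence is that S01 is a table-filling slip. Its action is the stock entry on nearly every row of Table 4-7. The two formal Safety Set definitions agree with each other, and a careful programmer would follow them. Adverse events are to be reported by treatment received, and an undosed patient has received none. Randomisation and first dose both fall at Visit 3 (Protocol 4.1), so there may be few such patients or none.

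This limits the likelihood and size of the problem but does not remove the contradiction. The table does change its action where that is intended: codes I24 and D05 remove the patient from every analysis. S01 concerns only undosed patients, so its action has no other reading.

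On the label, Protocol 7.1.1.2 is a data-collection rule and defines no analysis set. The parenthesis in SAP 2.6.1 ties screen failure to eligibility and screening procedures, which favours reading it as patients who are not randomised. Serious adverse events must be reported from consent onward with no exception for screen failures (Protocol 8.2.2), so the gap in recording is not total. These points stand, and they make the label a secondary matter.

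A reader might infer more: that the screen-failure label takes refusals out of the primary comparison, breaks the intent-to-treat principle and turns 12/30 = 40.0% into, say, 12/28 = 42.9%. The documents do not support this. No section removes screen failures from the FAS, S01 itself keeps the undosed patient there, and SAP 2.6.1 expects untreated patients among those randomised.

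**Conclusion.** S01 is wrong as written. It contradicts the one-dose condition in both documents and, if followed, lowers adverse event rates and mean exposure. With an assumed one to three undosed patients in an arm of 30, an event in 15 patients reads 50.0% in place of 51.7% to 55.6%. That range rests wholly on the assumed count; with no undosed patients the effect is nil.

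The screen-failure wording is a real but lesser conflict over disposition and data collection: one patient can be both a screen failure and a member of the FAS. The FAS response denominator is not in conflict. The SAP does not impute missing Hb and does not spell out that a patient with no post-baseline Hb is a non-responder, but SAP 2.5 still makes the number in the FAS the default denominator. The point merits correction because it is cheap and clear, not because it threatens the primary result.

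**What to change.** 1. **SAP Table 4-7, code S01.** Change the action to: report as a protocol deviation, keep in the FAS, leave out of the Safety Set. This is one table cell.
2. **Protocol 7.1.1.2 and SAP 2.6.1.** Define a screen failure as a consented patient who is not randomised. Align the Screening Log sentence in Protocol 6.5.1 and its copy in SAP 3.1. A randomised, never-dosed patient then no longer falls under the recording exemption in Protocol 8.1.1.

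The cost is a few sentences. Adverse event percentages will be slightly higher wherever undosed patients exist. The second change will not add events to the treatment-emergent tables, which start at first dose. Nor will it produce Hb values, since withdrawn patients have no further planned assessments under any label (Protocol 7.1.3.1). Its benefit is consistent disposition and data collection.
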